## **10. OWNERSHIP OF DATA**

10.1 The Study Data and all copyrights therein shall be the property of the Sponsor, subject to the rights of Novartis as specified in Section 11.

10.2 The Sponsor shall ensure that the Study Data are kept in orderly, safe and secure storage in accordance with regulatory requirements for document retention following the local archiving regulations for such data.

10.3 The Sponsor shall grant Novartis access to all Study Data generated in the course of the Study at no additional cost. Novartis shall have the right to make copies of the Study Data. Notwithstanding any other provision of this Agreement, Novartis and its Affiliates and their licensees or sublicensees shall have the right to use the Study Data for all purposes,

including, but not limited to, regulatory purposes (including filing), patent purposes, and publication referencing purposes at no additional costs.

- 10.4 Sponsor shall ensure that patient informed consent identifies all anticipated purposes for use of Study Data and shall ensure patient informed consent permits the sharing of Study Data with Novartis, its Affiliates and any successors and assigns of either party, including those located outside the European Economic Area. In obtaining and documenting the patient informed consent, Sponsor shall comply with the applicable regulatory requirement(s) and laws, and shall adhere to ICH GCP and to the ethical principles as laid out in the Declaration of Helsinki.

## **11. INTELLECTUAL PROPERTY**

- 11.1 Apart from any copyright in the Study Data any Invention, whether patentable or not, made by the Sponsor, its employees and agents and any other persons assisting with the conduct of the Study which relates to the Study Drug and any related Intellectual Property thereto shall be assigned to Novartis ("**Novartis Intellectual Property**").
- 11.2 Copyright in the Study Data and any Invention, whether patentable or not, made by the Sponsor, its employees and agents and any other persons assisting with the conduct of the Study arising from the performance of the Study other than an Invention constituting Novartis Intellectual Property pursuant to Section 11.1 above shall be the property of the Sponsor ("**Sponsor Intellectual Property**"). The Sponsor may agree to apportion ownership of the Sponsor Intellectual Property to Subcontractors and third parties at its discretion. The Sponsor shall grant to Novartis and its Affiliates a non-exclusive, perpetual, fully paid-up, royalty-free, worldwide license, with the right to sublicense, to use such Sponsor Intellectual Property for any purposes and an exclusive first option as well as a right of first refusal to an exclusive, world-wide license (with the right to grant sub-licenses) to exploit such Sponsor Intellectual Property.
- 11.3 Sponsor agrees to, and to cause its employees and collaborators and the Principal Investigator to, execute promptly all documents and take all such other action as may reasonably be requested by Novartis to permit Novartis to obtain the benefit of its rights under this Agreement.
- 11.4 Sponsor shall ensure that the Principal Investigator and the Sponsor's employees and collaborators involved in the Study will comply with its obligations under this Agreement.

## **12. STATUS OF THE PARTIES**

- 12.1 Each party is acting hereunder as an independent contractor. No provision of this Agreement shall be deemed to constitute any party as the agent, employee, partner, joint venture, or legal representative of any other party for any purpose whatsoever. No party is granted any express or implied right or authority to assume, or to create, any obligation or responsibility, or to execute any agreements or to make any commitments verbally or in writing for or on behalf of, or in the name of, any other party in any manner or thing whatsoever without that other party's express written consent.

## **13. TERMINATION**

- 13.1 This Agreement may be terminated by either party for any reason upon not less than thirty (30) days' written notice.
- 13.2 Either party may terminate this Agreement in the event that 1) the other party commits a material breach and fails to remedy such breach within thirty (30) days from the receipt of a

notice informing the breaching party of its failure to comply with its obligations under this Agreement or any of the Annexes, or 2) as per Section 3.9.

#### **14. CONSEQUENCES OF TERMINATION**

14.1 Upon termination of Novartis' involvement in this Agreement for whatever reason all Novartis Information shall be returned to Novartis, subject to any regulatory and ethical requirements.

14.2 Within thirty (30) days following termination or completion of the Study, all unused Study Drug provided by Novartis shall be returned to Novartis at Novartis' expense, subject to the provisions of Annex 4.

14.3 In case of termination by the Sponsor according to Section 13.1 or 13.2, the Sponsor will provide Novartis with access to all Study Data including computer data files as well as any relevant software and source codes to enable Novartis to retrieve and satisfactorily access all computerized data. For purposes of this clause, Personal Data is excluded from the obligation of disclosure. In addition, the Sponsor shall provide Novartis with an abbreviated TPSR or abbreviated final report. Furthermore, Sponsor shall submit the study-related publications based to Study Data obtained before termination to scientific congresses and/or journals and Novartis shall have the right to review the draft(s) in accordance to the section 7 of the Agreement. Finally, pursuant to the section 18 of the Agreement, termination by the Sponsor will not affect all the rights and obligations which are intended to survive termination of this Agreement.

14.4 Upon the effective date of termination according to Section 13.1, or 13.2 the Sponsor shall conduct an accounting, subject to verification and approval by Novartis. Within thirty (30) days after receipt of adequate documentation setting forth the results of such accounting, Novartis will make payment to the Sponsor (in no event exceeding the difference between the maximum amount specified in Section 4.1 and the total amount paid previously by Novartis to the Sponsor under or in connection with this Agreement) for:

- (a) All Study activities properly rendered and costs properly incurred by the Sponsor according to the terms of this Agreement up to the effective date of termination and not yet paid for; and
- (b) Reasonable non-cancelable commitments properly incurred by the Sponsor for the conduct of the Study prior to receipt of notice of termination.

14.5 Notwithstanding anything else in Section 14.4, in case of termination by Novartis due to Sponsor's material breach, Novartis shall owe no further payment to the Sponsor.

14.6 The Sponsor will refund to Novartis within thirty (30) days following the termination date any funds advanced to it but not expended or irrevocably committed by the Sponsor prior to the date of termination.

#### **15. WARRANTIES**

15.1 The Sponsor represents and warrants to Novartis that it is not a party to any agreement which would prevent it from fulfilling its obligations under this Agreement and that during the term of this Agreement the Sponsor will not enter into an agreement to undertake studies

which would in any way restrict its ability to undertake the Study or fulfill its obligations under this Agreement.

- 15.2 The Sponsor warrants and represents to Novartis that it has the full right and authority to enter into this agreement, and that it is not aware of any impediment which would inhibit its ability to perform the terms and conditions imposed on it by such agreement.
- 15.3 The Sponsor warrants and represents to Novartis that the Sponsor's policies applicable to the performance of the Study are consistent with the terms of this Agreement and Protocol.
- 15.4 For the purpose of transparency, and to ensure Novartis is providing adequate funding, Sponsor shall disclose to Novartis any other funding received from a third party to undertake the Study, and as the case may be, Sponsor shall disclose the amounts received from the other supporting party. Sponsor shall disclose this information to Novartis along with the request for support.

## 16. DISCLAIMER

NOVARTIS AND/OR ITS AFFILIATES PROVIDES ALL MATERIALS HEREUNDER [ , INCLUDING STUDY DRUG].] "AS IS" AND THEY MAKE NO WARRANTY OF ANY KIND, EXPRESS OR IMPLIED, CONCERNING SUCH MATERIALS OR THEIR MERCHANTABILITY OR FITNESS THEREOF FOR ANY PURPOSE, INCLUDING BUT NOT LIMITED TO NONINFRINGEMENT OF ANY THIRD PARTY INTELLECTUAL PROPERTY RIGHTS. UNDER NO CIRCUMSTANCES SHALL NOVARTIS AND/OR ITS AFFILIATES BE LIABLE IN ANY MANNER FOR CONSEQUENTIAL, INCIDENTAL, SPECIAL, OR INDIRECT DAMAGES. Any advice furnished by Novartis and/or its Affiliates is given free of charge and Novartis and/or its Affiliates assumes no obligation or liability for the advice given or the results obtained and any such advice shall not constitute a warranty as to any matter, all such advice being given and accepted at the recipient's risk.

## **19. ENTIRE AGREEMENT**

This Agreement (together with any documents referred to herein) constitutes the entire and only agreement and understanding between the parties with respect to its subject matter and supersedes any previous agreements, understandings, or arrangements between the parties in respect of the Study (whether oral or written). Any claimed representation, promise or condition in connection with the subject matter of the Agreement that is not incorporated herein shall not be binding upon any party. No modification, extension, waiver, or other variance of any provision hereof, or any release of any right hereunder, shall be valid or binding unless the same is in writing and signed by all parties. In the event of any conflict between the operative provisions of this Agreement and the Annexes hereto, the operative provisions of this Agreement shall govern.

## **20. AMENDMENT**

This Agreement and the Protocol may be extended, renewed or otherwise amended at any time by the mutual written consent of parties hereto.

## **21. FORCE MAJEURE**

Neither the Sponsor nor Novartis shall incur any liability to any other party in the event of non-performance or delay in the performance of its obligations hereunder if caused directly or indirectly by strikes, lockouts, riots, sabotage, act of war or piracy, destruction of essential equipment by fire, explosion, storm, flood, earthquake, failure of power supplies or transport facilities, failure of agents, or sub-contractors or any other event or circumstances whatsoever beyond the reasonable control of the party liable to perform for a period equal to any such non-performance or delay. However, the party affected shall use all reasonable endeavours to limit the amount of non-performance or delay in performance of its obligations hereunder.

## **22. WAIVER**

The failure of a party at any time to require full or partial performance of any provisions of this Agreement will not affect in any way the full right of that party to require that performance subsequently. Any waiver of a breach of this Agreement must be in writing signed by the party granting the waiver.

## **23. SEVERABILITY**

Any provision of this Agreement which is declared void or unenforceable by any competent authority or court shall to the extent of invalidity or enforceability be deemed severable and not affect the provisions of this Agreement which shall continue unaffected.

## **24. ASSIGNMENT**

Neither party may assign its rights and obligations under this Agreement without the other party's prior written consent, except that Novartis may (a) assign its rights and obligations under this Agreement or any part hereof to one or more of its Affiliates; or (b) assign this Agreement in its entirety to a successor to all or substantially all of its business or assets to which this Agreement relates. Any permitted assignee will assume all obligations of its assignor under this Agreement (or related to the assigned portion in case of a partial assignment). Any attempted assignment in contravention of the foregoing will be void. Subject to the terms of this Agreement, this Agreement will be binding upon and inure to the benefit of the parties and their respective successors and permitted assigns.

## **25. NO TRANSFER OF PROPRIETARY RIGHTS NOT SPECIFIED**

It is agreed that neither Novartis nor the Sponsor transfers to the other by operation of this Agreement any patent right, copyright, or other proprietary right of either party, except as specifically set forth herein.

## **26. LIABILITY**

Subject to the provisions of Section 28.2, the Sponsor as the Sponsor of the Study shall be liable for all damages incurred by a patient arising out of the performance of the Study.

## **27. INSURANCE**

27.1 The Sponsor as the sponsor of the Study agrees to take out adequate clinical trial insurance or make alternative arrangements as is necessary and required by applicable regulatory requirements to cover its obligations as Sponsor of the Study including, but not limited to, providing full compensation (including indirect losses) to participants in the Study suffering injury or death or loss caused by the administration of drugs or any clinical intervention or procedure in accordance with the relevant Protocol and all legal requirements laid down by local regulations.

27.2 Upon Novartis' request the Sponsor shall provide evidence of such insurance or alternative arrangement.

## **28. INDEMNIFICATION**

28.1 The Sponsor agrees to indemnify and hold harmless Novartis, its Affiliates and their respective employees, directors, officers, representatives, sub-contractors, and agents from and against any loss, damages, liabilities, reasonable costs and expenses (including reasonable attorney's fee and expenses), incurred in connection with any claim, proceeding, or investigation arising out of this Agreement and of this Study, except to the extent as provided under Section 28.2.

28.2 Novartis agrees to indemnify and hold harmless the Sponsor and its employees, directors, officers, representatives, sub-contractors and agents from and against any loss, damages, liabilities, reasonable costs and expenses (including reasonable attorney's fee and expenses) incurred in connection with any claim, proceeding, or investigation arising out of this Agreement (hereinafter referred to as "Claims") to the extent that such Claims arise from [(i)] the willful wrongful act or omission or the negligence of Novartis; or (ii) a product liability issue regarding the Study Drug furnished to the Sponsor under this Agreement, provided the Study Drug has been used in accordance with the Protocol.

**List of Attachments:**

- Annex 1: Final Signed Protocol for the Study (dated xxxxx)**
- Annex 2: Key Contacts**
- Annex 3: Payment Plan**
- Annex 4: Drug Supply: Table of activities and responsibilities**
- Annex 5: Safety data collection and reporting responsibilities**
- Annex 6: Cover sheet for use when transferring safety information**
- Annex 7: Signed Attestation Form**

**ANNEX 1-FINAL NOVARTIS APPROVED PROTOCOL FOR THE STUDY**

## Investigator Initiated Trial

**(1) Title of study**

Effects of Ranibizumab to delay or regression non-proliferative diabetic retinopathy(NPDR) with DME assessed by microaneurysm changes: A pilot study

**(2) Institution**

Dept. of Ophthalmology, Wonkwang Univ. School of Medicine, Icksan Jeonbuk, South Korea

**(4) Study Design**

single center, prospective, interventional, one arm, pilot study

**(5) Objectives**

**Objectives:** To evaluate the effects of intravitreal Ranibizumab injection on microvascular changes in eyes of mild-to-moderate NPDR with DME.

**Primary objective:** To compare microvascular changes assessed by microaneurysm counts in eyes of mild-to-moderate NPDR with DME after intravitreal Ranibizumab injection from baseline through 6 months after treatment.

**Secondary objectives:** To investigate other efficacy endpoints including other microvascular, anatomical, visual acuity change and safety in mild-to-moderate NPDR with DME after intravitreal Ranibizumab injection from baseline through 6 months after treatment.

**(6) Study rationale**

Diabetic retinopathy is the leading disease that causes acquired vision loss after 20 by making diabetic macular edema and neovascularization. In recent young generation, as prevalence of type 2 diabetes is growing, the burden of sight-threatening retinopathy is increasing on trend.

Pathologically, angiogenesis is a main cause that destroys the structure of the eye and induces the visual function disorder as VEGF playing an important role in increasing the migration and proliferation of endothelial cells and increasing the permeability of the blood vessels.

VEGF is made from the endothelial cells of retinal tissue, perivascular cells, pigment endothelial cells by hypoxia. And hypoxic condition of intraocular tissues is a key regulator of intra ocular angiogenesis by VEGF, the balance between VEGF and angiogenesis inhibitors determines the neovascular proliferation in diabetic retinopathy.

VEGF is also inducing the expression of cell-to-cell contact molecule (intracellular adhesion molecule-1, ICM-1) and the adhesion of leukocytes to help the inflammatory response, as mediator which destroys the blood retinal barrier, affecting the protein of tight junctions, making a microaneurysm and increasing permeability of capillary, that makes the liquid leakage and macular edema.

Microaneurysm is the earliest clinical manifestations, the saccular local lesion that perivascular cells protruding in

damaged areas on the capillary wall. According to Stitt AW et al, diabetic microaneurysm is non-functioning extrusion of the vascular system from the deep part of inner retinal capillary plexus.

It is sometimes disappeared by being blocked with blood clots, on the other hand, new microaneurysm is occurred in the other vascular bed structure.

Through these changes, we know the course of a diabetic retinopathy and it is known that the generation rate of microaneurysm is associated with the clinically significant progression of macular edema (CSME) in mild-to-moderate nonproliferative diabetic retinopathy .

In addition, the number of microaneurysm is an important prognostic indicator which can estimate the progression or regression of diabetic retinopathy, as predicting whether becoming better or worse in diabetic retinopathy.

Kohner and Sleightholm^13 describe this concept at first time in 1986, its association with the number of microvascular flow and the severity of diabetic retinopathy. In recent years it is reported that measuring the number of microaneurysm and the turnover rate associated with the appearance or disappearance of microaneurysm, are predictors in progression of diabetic retinopathy and macular edema.

To delay the progression of diabetic retinopathy and to improve macular edema, the laser photocoagulation have been the important role. Although the laser photocoagulation have had treatment effect in the diabetic retinopathy by reducing the amount of VEGF in micraneurysm and by degenerating the neovascularization after laser therapy, there was a problem that has many limitations - peripheral visual field defects, night blindness, progression of macular edema etc., and that the disease does not cured in a good time because of limits of laser therapy due to cataract, vitreous hemorrhage and turbidity. As an alternative method to solve these limitations, there is an anti-VEGF therapy. According to a previous study result, intraocular injection of Bevacizumab inhibits occurring of neovascularization by blocking the VEGF receptor .

Recently, several studies have been reported that when injected intravitreal anti-VEGF, macular edema is improved and neovascularization is inhibited, by reducing the leakage of neovascularization.

Especially, Leicht SF et al reported the number of microaneurysms and turnover rate in NPDR(non-proliferative diabetic retinopathy) patients injected with Ranibizumab. And the result showed entire number of the microaneurysms and turnover rate are decreased, which could be mean the regression of diabetic retinopathy and it could decide the therapeutic effect.

On this study, through the fluorescein fundus angiography, the average number of microaneurysms was significantly decreased after intravitreal injection of anti-VEGF therapy ( $p < 0.05$ ). The decrease of  $35.70 \pm 24.79\%$  in the treatment group was statistically higher than  $13.95 \pm 38.21\%$  in the control group of the fellow eye ( $p < 0.05$ ).

The result is found because decreased concentration of intravitreal VEGF inhibits the progression of diabetic retinopathy, such as endothelial cell proliferation and endothelial cell damage on retinal capillary and perivascular cells.

Sjølie AK et al reported up-regulation of VEGF occurring microaneurysms causes endothelial cell proliferation and inflammation and effusion reaction, so anti-VEGF is effective in early diabetic retinopathy. But there is less effectiveness in late diabetic retinopathy as it reaches the non-changing point. Also Kohner EM et al reported diabetic retinopathy lesions are reversible and could be delayed in early diabetic retinopathy.

So far, changes of microaneurysms in late diabetic retinopathy is uncertain, and if there would be a finding according to anti-VEGF therapy, we could get a clue of surrogate marker which represents treatment results in diabetic retinopathy.

This study was designed to find the clinical evaluation and reduction rate through fluorescein angiography as microaneurysm examination tools to research NPDR with DME treatment results assessed by microaneurysm counts, timely monitored with anti-VEGF therapy.

## **(7) Number of centers & patients, inclusion/exclusion criteria**

-25 patients, 1 center

- Inclusion criteria

- Patients (Male & female) > 40 years of age

- Type 2
- Best corrected visual acuity > 20/200 (Snellen equivalent using Early Treatment Diabetic Retinopathy Study chart)
- Central retinal thickness of > 300 um on optical coherence tomography
- Nonproliferative diabetic retinopathy (NPDR) with diabetic macular edema

- Exclusion criteria

- PDR – NVE & NVD
  - Early PDR – New vessels ; and criteria not met for high-risk PDR
  - High risk PDR – New vessels on or within one disc diameter of the optic disc (neovascularization of the disc) > standard photograph 10A with or without vitreous or preretinal hemorrhage ; or vitreous and/or preretinal hemorrhage accompanied by new vessels, either NVD < standard photograph 10A or new vessels elsewhere (NVE) > 1/4 disc area
- Vitreous hemorrhage
- Prior intraocular operation history.
  - Pars Plana Vitrectomy, RD surgery, recent (4 months) cataract Op, et al
- Prior any intravitreal injection history.
  - Lucentis, Eylea, Macugen, Avastin, Triamcinolone et al
- Prior pan retinal photocoagulation (PRP) or sector scatter photocoagulation was done.
- Uncontrolled hypertension.
- Uncontrolled glaucoma.

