**(9) Study duration**

**Until 30 Jul 2017(CSR submission)**

## **(10) Methodology**

Primary and secondary endpoints:

Primary endpoint:

To compare other visual acuity, anatomical changes after intravitreal Ranibizumab injection from baseline through 6 months after treatment.

i) The changes in best corrected visual acuity (BCVA) using ETDRS chart. ii) The central macular thickness - Circle Diameters : 1 mm ETDRS by spectralis OCT ; Heidelberg Engineering.

Secondary endpoints:

To compare microaneurysmal changes and perifoveal non-perfusion area and safety after intravitreal Ranibizumab injection from baseline through 6 months after treatment.

i) The total number of microaneurysm by fundus photo using Retmarker DR(version 1.0.2) software.

ii) The microaneurysm formation rate : Number of new MAs detected/month. iii) The microaneurysm disappearance rate : Number of MAs that resolved/month. iv)The microaneurysm turnover. v) Perifoveal non-perfusion area in FAG (mm^2) using ImageJ software (version 1.52a) by FAG image.

vi) Safety parameters : Systemic adverse events (MI, CVA, etc), Ocular adverse events (retinal detachment, RPE tear, endophthalmitis, uveitis, vitreous hemorrhage, subretinal hemorrhage, cataract , IOP elevation, etc).

single center, prospective, interventional, one arm, pilot study

Evaluation Participants will be evaluated with a full ocular examination at each visit (VA measurement, tonometry, slit lamp exam). Fluorescein angiography (FA) will be performed at baseline, at 3 months after baseline and at the last visit(6 months after baseline), and OCT will be performed monthly (baseline and 1, 2, 3, 4, 5, 6 months from baseline).

The MAs and perifoveal non-perfused areas in individual retinas were evaluated at 6 months using fundus photography and FA imaging. The Retmarker (version 1.0.2 by Retmarker Ltd, Coimbra, Portugal) software was used for automatic measurement and analysis of changes in number and extent of MAs on fundus photographs and to calculate the total number and turnover of MAs.

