### **Statistical Analysis Plan**

Result analysis The investigators compare the differences between at baseline, at 3 month, and at 6 month. Statistical analyses will be performed using SPSS ver.18.0 (SPSS Inc., Chicago, IL, USA). Kolmogorov-Smirnov test was applied to test for normality of sample group data. The repeated measures analysis of variance with Bonferroni correction was used to analyze continuous outcome measures, including BCVA, CRT, total number of MAs, MA formation rate, MA disappearance rate, MA turnover, and perifoveal non-perfused area, before and after completion of 6 months of IVR therapy. A P-value <0.05 was considered statistically significant.

Table 1. Schedule of visits and procedures

Note: X = procedure to be performed, R = rescue treatment	Baseline Month 0 (Visit 1)	Month 1 (Visit 2)	Month 2 (Visit 3)	Month 3 (Visit 4)	Month 4 (Visit 5)	Month 5 (Visit 6)	Month 6 (Visit 7)
Informed consent	X						
Review eligibility criteria	X						
Demographics	X						
ETDRS BCVA	X	X	X	X	X	X	X
Slit lamp exam	X	X	X	X	X	X	X
IOP	X	X	X	X	X	X	X
OCT	X	X	X	X	X	X	X
Color Fundus Photo	X	X	X	X	X	X	X
FA	X			X			X
ICGA	X			X			X
Lucentis® injection	X	X	X	X	X	X	
Adverse events	X	X	X	X	X	X	X

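### The OCT reading that qualifies an eye (> 300 um) appears also to be the baseline for the thickness endpoint, so part of any reported thinning may be regression to the mean

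*Combined protocol and SAP*

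**What the plan says.** Section (7) sets a one-sided thickness criterion, "Central retinal thickness of > 300 um on optical coherence tomography". It names no visit, device or scan area.

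Section (10), Methodology, lists under the primary endpoint "The central macular thickness - Circle Diameters : 1 mm ETDRS by spectralis OCT ; Heidelberg Engineering", analysed as "anatomical changes after intravitreal Ranibizumab injection from baseline through 6 months after treatment". Its scan schedule is "OCT will be performed monthly (baseline and 1, 2, 3, 4, 5, 6 months from baseline", so one scan is planned before treatment.

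Table 1, in the Statistical Analysis Plan, has no screening column. The row "Review eligibility criteria" is marked only at Month 0 (Visit 1), where OCT and the first injection are also marked.

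The Statistical Analysis Plan compares baseline, month 3 and month 6. For continuous outcomes, including CRT, it uses repeated measures ANOVA with Bonferroni correction at P<0.05. It describes no repeat scan and no adjustment for selection. Section (4) describes the study as "single center, prospective, interventional, one arm, pilot study", with 25 patients under section (7).

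Section (5) makes microaneurysm count the primary objective, whereas section (10) lists visual acuity and thickness under the primary endpoint.

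**The concern.** A single thickness reading is the eye's usual level plus that day's deviation (scan error and natural fluctuation). A rule that keeps only readings above 300 um keeps eyes near the cut when the deviation is upward and drops them when it is downward. If the same reading is then the baseline, the baseline mean is too high and the follow-up mean is not, so an average fall appears without any drug effect. Both the month 3 and the month 6 contrasts carry it, and with one arm nothing in the data separates it from treatment.

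At stake are the size of the thinning estimate and the error rate of its test, always in the direction of benefit. The matter is related to the lack of a control group but not identical to it: this part comes from the entry rule and can be reduced without adding an arm.

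**Working it through.** The plan gives no SD, repeatability, expected thinning or power, so it has no figure of its own to reproduce.

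**Inputs from the documents:** cut c = 300 um (section 7); n = 25 (section 7); one pre-treatment OCT (section 10, Table 1); comparisons at baseline, month 3 and month 6 at 0.05 (Statistical Analysis Plan), taken as two-sided.

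**Assumptions, not in the documents:** readings in candidate eyes before the cut are normal with mean m = 300, 350 or 400 um and total SD s = 100 um. The within-eye SD between visits, w, is 20, 30 or 40 um, independent between visits. The entry and endpoint thickness are the same measure.

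**Expected artificial fall:** (w²/s) × φ(z)/(1−Φ(z)), with z = (c−m)/s.

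- m = 300: z = 0, ratio = 0.3989/0.5000 = 0.798
- m = 350: z = −0.5, ratio = 0.3521/0.6915 = 0.509
- m = 400: z = −1, ratio = 0.2420/0.8413 = 0.288

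w²/s is 4, 9 and 16 um for w = 20, 30 and 40. For example, at m = 350 and w = 30: 9 × 0.509 = 4.6 um.

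| Candidate mean | w = 20 | w = 30 | w = 40 |
|---|---|---|---|
| 300 um | 3.2 um | 7.2 um | 12.8 um |
| 350 um | 2.0 um | 4.6 um | 8.2 um |
| 400 um | 1.2 um | 2.6 um | 4.6 um |

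With scan error alone (w = 10), w²/s = 1 um, and the fall is 0.8, 0.5 and 0.3 um.

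The correlation between two untreated readings of an eye is 1 − w²/s², so w = 20 to 40 means 0.96 to 0.84. A lower correlation of 0.70 would give 23.9, 15.3 and 8.6 um at means 300, 350 and 400, and 4.2 um at mean 450.

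**Rejection rate at 0.05 with no true change** (simulation, n = 25; ranges run over w = 20 to 40):

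| Candidate mean | One paired t test, uncorrected | Repeated measures ANOVA, overall test | Any of three pairs, Bonferroni |
|---|---|---|---|
| 300 um | 8.6% to 20.4% | 8.3% to 19.1% | 7.5% to 17.5% |
| 350 um | 6.3% to 10.8% | 6.1% to 10.3% | 5.4% to 9.2% |
| 400 um | 5.6% to 6.6% | 5.2% to 7.0% | 4.7% to 6.0% |

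The last two columns follow the planned analysis.

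**After separating the scans.** If entry is decided on one OCT and baseline comes from another with independent deviation, the simulated fall is about 0 um and the paired test rejects in about 5% of trials.

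**Share of eyes whose separate baseline would be at or below 300 um.** At m = 300 and w = 40 the correlation is 1 − 1600/10000 = 0.84. Both readings exceed 300 with probability 1/4 + arcsin(0.84)/(2π) = 0.409, so the share is 1 − 0.409/0.5 = 18%. At m = 400 and w = 20 it is about 3%.

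**The case against.** The strongest reply is that the key premise is an inference. No sentence says that the Visit 1 OCT qualifies the eye. Reviewing eligibility can mean checking scans already in the chart, and since entry requires macular edema, an earlier diagnostic OCT is plausible. This stands: the plan is silent on the qualifying scan, and the overlap is how Table 1 reads, not something it states.

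Three further points also stand.

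- The criterion speaks of central retinal thickness, the endpoint of central macular thickness in a 1 mm circle, and the Statistical Analysis Plan of CRT. The documents do not equate them. If they differ, the bias shrinks with the correlation of their deviations.
- The upper figures need a candidate mean of 300 um. With SD 100 that puts half of the candidates at or below the cut and 16% below 200 um, which is hard to square with eyes that must have macular edema.
- The larger figures depend on natural fluctuation. Any slow fluctuation shared by an earlier scan and the Visit 1 scan stays in the comparison and can be removed only with untreated eyes.

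The reply does not remove the point. The direction is certain whenever one varying reading serves both purposes, and the plan names no other qualifying scan.

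**Conclusion.** The concern holds conditionally. If the Visit 1 reading both admits the eye and serves as baseline, and the entry and endpoint thickness are one measure, part of the reported thinning is regression to the mean. On the assumed SDs the plausible size is a few micrometres. The false-positive rate of the planned analysis stays at or below about 10% at candidate means of 350 um or more, and reaches 17% to 19% only in the least favourable case at mean 300.

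A reader might infer more, in three ways that the documents do not support. They do not show that the same scan is certainly used twice. They do not show that the observed thinning will be mostly artefact, since they give neither an expected effect nor a repeatability figure. And separating the scans does not remove the bias entirely.

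Whether a primary result is affected depends on reconciling section (5) with section (10). Thickness is a tested outcome either way. This is a cheap improvement to a small pilot, not a fault that invalidates it.

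**What to change.** In section (7), state that the > 300 um criterion is judged on an OCT already taken before Visit 1 where one exists, and whether it is the same 1 mm measure as the endpoint. The threshold itself is unchanged.

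In the Statistical Analysis Plan, state that:

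- the Visit 1 OCT is the analysis baseline whatever its value, and the qualifying reading is not used as baseline;
- eyes with no earlier OCT, whose Visit 1 scan must serve both purposes, are flagged, and the thickness change is reported with and without them;
- the separation removes only variation that is independent between the two scans, and any remainder is a limit of the one-arm design.

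A second scan on the same day is not worth adding: it would remove only scan error, under 1 um on the figures above.

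The cost is a few sentences and no new procedure. The downside is that about 3% to 18% of eyes with separate scans, under these assumptions, would have a baseline at or below 300 um, and the reported thinning would be slightly smaller.
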